## **E. Definition of Primary and Secondary Outcomes/Endpoints**

### **Primary:**

- Analgesic requirements, rendered as opiate equivalents, at 12, 24 and 48 hours, and the 24 hours preceding both 72 and 96 hours postoperatively.

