#### Specific Aims:

1. Evaluate the utility of BESB in cardiac surgical patients by assessing the pain scores, opioid consumption, and complications related to BESB.
2. Compare intra- and postoperative opioid use in patients receiving BESB vs. matched historical controls who did not receive BESB in the ERAS program.
3. Compare clinical outcomes between the 2 groups: duration of mechanical ventilation, time to mobilization, pain scores (median pain score per period), intensive care unit length of stay (LOS), incidence of postoperative nausea and vomiting, postoperative complications, hospital LOS, readmissions, mortality, recovery to baseline activity and sleep post discharge, total and rescue opioid pain medication requirements.
4. Evaluate quality of sleep and activity with (Fitbit™) smart watch device of patients receiving BESB during the postoperative period.

**Hypothesis:** The investigators hypothesize that BESB is efficacious with respect to pain control and will lead to a 15% or greater reduction of consumed opiate equivalents at 12, 24 and 48 hours, and the 24-hour period preceding both 72 and

96 hours postoperatively compared to matched historical controls who received standard of care pain management (systemic opioid therapy).

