Indeed, given these considerations, our group recently investigated the feasibility of performing these blocks bilaterally in a pediatric cardiac surgical population undergoing sternotomy-based procedures (IRB-P00031524). At the conclusion of this 10-patient pilot, our group found that performing these blocks was technically feasible, requiring 30 minutes or less of OR time, resulting in no known complications. Furthermore, our data suggested an approximate 25% reduction in rescue opioid requirements in the first 48 hours amongst the erector spinae group ( $p=0.048$ ).

During the short time required to complete our pilot study, several additional adult studies of improved size and quality have been published demonstrating favorable outcomes with this block for a variety of indications, including post-sternotomy care. As such, it has effectively become an accepted practice in the larger community and here at BCH as well, with surgeons, anesthesiologists, and families frequently requesting an ESB (unilateral or bilateral) as a part of the care they either provide or receive. We believe we have reached a point of clinical equipoise in relation to the existing standard of systemic opioid therapy and seek to evaluate the relative efficacy of this technique in a pediatric cardiac surgical population at BCH.

In order to best evaluate the efficacy of this block in the pediatric cardiac population, a blinded, randomized and controlled trial would be ideal. However, given that randomization could be challenging and the fact that blinding would not be feasible, we believe an observational prospective cohort study is most appropriate at this time.

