As such, we propose to evaluate the comparative efficacy of BESB versus matched historical controls who received standard of care pain management (systemic opioid therapy) for patients undergoing cardiac surgery via sternotomy by means of a single arm, open label, interventional study that will compare as the primary outcome rescue analgesic requirements, rendered as opiate equivalents, at 12, 24 and 48 hours, and the 24 hour period preceding both 72 and 96 hours postoperatively. 'Efficacy' will be considered as a threshold of clinical significance being defined as a 15% difference). In addition to the primary endpoint, we plan to evaluate the duration of intubation, length of ICU stay, median pain scores, incidence of PONV (postoperative nausea and vomiting; 0-6h, 6-12h and overall), time to mobilization and adverse events between these groups. Postoperative data collected from standard clinical follow-up tools, such as return to baseline sleep and activity status as well as pain medication requirements at home, will also be compared. In addition, we plan to evaluate the quality of sleep and activity with a smart watch (Fitbit™) during the perioperative period in the BESB group only.

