As previously noted, our group recently investigated the feasibility of performing BESBs in a pediatric cardiac surgical population undergoing sternotomy-based procedures at this institution. At the conclusion of this 10-patient pilot, we found that performing these blocks was technically feasible -- requiring 30 minutes or less of OR time -- and resulted in an approximate 25% reduction in rescue opioid requirements in the first 48 hours amongst the BESB group ( $p=0.048$ ). There were no significant adverse events noted during this pilot with the exception of a single instance of a kinked (but useable) catheter.

While the numbers at BCH are relatively small, retrospective analyses of ESBs performed in this institution in non-cardiac surgery have demonstrated no evidence that this block type is associated with any greater risk than that demonstrated by aggregate block data from the various pediatric regional anesthesia registries. Information currently available suggests that regional blockade, when performed properly, carries a very low risk of morbidity and mortality in appropriately selected infants and children. Furthermore, we have found no evidence of increased adverse events present in the ESB patients when compared to patients receiving other regional anesthetics in our local analysis. Indeed, two abstracts addressing the safety and efficacy of ESB blocks in BCH patients have recently been accepted for presentation at the major regional anesthesia conference.

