In addition to observational tools and subjective scoring, patient functional status (activity, sleep quality and other measures) will be assessed by actigraphic analysis using the Fitbit™ Charge 3 smartwatch. A Fitbit™ will be placed on the non-dominant arm, if possible, after extubation on the day of surgery. The Fitbit™ will remain on the patient until discharge from the hospital (which on average is about 5 days post-op) and the actigraphic data subsequently will be downloaded to the secure research database and the data wiped from the device. If a study subject had an unforeseeable complication and they no longer progressed along the standard recovery path (e.g. re-intubation, return to ICU), or if the watch was interfering in clinical care in any way, the Fitbit™ would be removed.

Following primary data collection for the enrolled subjects, each subject will be matched by surgical procedure using the STS procedure code, to 2 patients within the cardiac surgery ERAS program QI database (IRB #P00029161 which allows retrospective data analysis of outcomes) by the research team. All patients recruited for this study are themselves already part of the enhanced recovery after cardiac surgery clinical program [QIP]. Matching will be performed 1:2 with respect to surgical procedure and diagnosis using the STS codes, within 30% of the study patient's age and according to gender (if possible) and will be blinded to outcomes. Thus, up to 90 additional patients will be included in this study, retrospectively in addition to the 45 study patients from the single arm interventional cohort study (BESB).

Groups will be compared for demographic data, risk factors (from the STS database), diagnosis, procedure and cardiopulmonary bypass and clamp times to ensure their similarities

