### **Secondary:**

- Analgesic requirements, rendered as total opiate equivalents, at 12, 24 and 48 hours, and the 24-hour period preceding both 72 and 96 hours postoperatively.
- Duration of intubation following OR exit.
- Duration of ICU stay following OR exit.
- Duration of inpatient admission.
- Median pain scores collected per standard of care (VAS, NRS, INRS, or FLACC) at 0-3h, 3-6h, 6-12h, 12-24h, 24-36h and 36-48h.
- Incidence of postoperative nausea and vomiting during the following time ranges: 0-6h, 6-12h, 12-24h, and overall
- Time to mobilization (e.g. up to chair, ambulation).
- Quality/Quantity of mobilization and sleep via postoperative actigraphy.
- Outcome and satisfaction measures associated with routine perioperative questionnaire responses.
- Adverse events. – catheter, hemodynamic instability during placement (new inotrope or vasopressor – including Ca, volume > 5ml/Kg, variation 10% baseline SBP and MAP)
- All major Society of Thoracic Surgeons (STS) standard indices of morbidity and mortality

\*Of note, all of the above data points are collected automatically (via the electronic medical record) for all patients, as a part of their routine clinical care, regardless of whether or not they participate in the study.

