## **K. Data Analysis Plan**

At the time of data analysis, de-identified datasets will be downloaded from the secure database and merged into secure statistical analysis tool for purposes of analysis. Missing data will be accounted for when the data is coded into respective variables.

Descriptive statistics will be generated in order to summarize demographic characteristics of patients enrolled. Data will be tested for normality using the Shapiro-Wilk test. Data will be presented as total n (%), means and standard deviations (SD) if the distribution appears normal, or medians and range when not.

Assuming normality, t-tests will be conducted to investigate the differences between the two exposure groups (to compare total opioid equivalents, time required to place the block, time to extubation, and time to discharge, etc.). If data does not appear to be normal, Wilcoxon Rank Sum/Mann-Whitney tests will be used for group comparisons. Repeated measure analysis will be used to compare pain scores over time between groups and when compared to baseline values. Adverse events and complications (if any) associated with the blocks will be recorded and categorized. Fisher's exact test will be used to compare the proportion of patients who reported adverse events between the two groups.  $P<0.05$  will be considered statistically significant.

Should a clinically significant effect be demonstrated, healthcare costs related to the surgical encounter for both groups will be approximated and compared in order to better assess the added value of the intervention in a more global fashion.

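### Five opioid windows are listed as primary with no decision rule, while the 80% power belongs to cumulative 0–96 h opioid use, which is on neither endpoint list

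*Combined protocol and SAP*

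**What the plan says.** Section E, Primary, lists "Analgesic requirements, rendered as opiate equivalents, at 12, 24 and 48 hours, and the 24 hours preceding both 72 and 96 hours postoperatively". The hypothesis in Section A is a "15% or greater reduction of consumed opiate equivalents at 12, 24 and 48 hours", continuing to the 24-hour periods before 72 and 96 hours. Section B says that the study will "compare as the primary outcome rescue analgesic requirements, rendered as opiate equivalents, at 12, 24 and 48 hours", followed by the same two late periods. None of these places names a lead window or says how many windows must succeed.

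The secondary list in Section E repeats the five windows for a differently labelled measure: "Analgesic requirements, rendered as total opiate equivalents, at 12, 24 and 48 hours" and the same late periods. Section K uses t-tests or rank-sum tests "to compare total opioid equivalents, time required to place the block, time to extubation, and time to discharge, etc", with P<0.05, no window and no multiplicity rule.

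Section L defines efficacious as at least a 15% difference in total opioid consumption at 96 hours, based on historical rescue opiate data. It sizes the study on square-root Total (96-hr) OME: a 0.18 difference, 80% power, 38 BESB and 76 controls. It adds that this size gives 87% power for a 0.16 difference in square-root 48-hr OME. Planned enrolment is 45 and 90.

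**The concern.** Two different definitions of success stand side by side. Section L rests it on one quantity, opioid use at 96 hours. Section A joins five windows with *and*, which reads most naturally as requiring all of them. These rules have different power, and the power statement belongs to an outcome that Section E does not list. In an open-label comparison with historical controls, a primary left this open could be settled after the results are known.

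The choice of window is not academic, because the sponsor's own pilot falls on either side of the 15% threshold according to the window. Two further ambiguities affect the same sentence: which opioid measure is primary (rescue, consumed, unqualified or total, depending on the section), and whether the 15% refers to OME or to its square root.

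**Working it through.** **Which outcome was powered.** In Table 2 (Section L), Total_OME exceeds the 48 h variable in both groups (ERAS 1.557 vs 1.134; BESB 1.346 vs 0.854). Total (96-hr) OME is therefore cumulative, not the 72–96 h window. It can be built as 0–48 + 48–72 + 72–96 h, but neither list in Section E names it.

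**Reproducing the plan's figures.** Two-sample t-test, two-sided 0.05, noncentral t with noncentrality δ/(SD·√(1/n₁+1/n₂)). The square-root term is 0.1987 at 38/76 and 0.1826 at 45/90.
- 96 h, δ = 0.18, SD 0.32: noncentrality 2.83 and power 80.1% at 38/76; 3.08 and 86.4% at 45/90.
- 48 h, δ = 0.16, SD 0.26: noncentrality 3.10 and power 86.7% at 38/76 (stated 87%); 3.37 and 91.7% at 45/90.

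The arithmetic is sound. The 12 h, 24 h, 48–72 h and 72–96 h windows have no stated power.

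**Illustration for five windows.** The documents give no between-window correlations, so these are assumptions. Eight equal-variance 12-hour blocks were summed into the five windows, each with the planned standardised effect 0.18/0.32 = 0.5625 (100,000 simulated trials per setting).

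| Block correlation | All-five power, 38/76 | All-five power, 45/90 | Any-window error, 38/76 |
|---|---|---|---|
| 0 | 41.5% | 55.2% | 20.1% |
| AR(1) 0.3 | 44.6% | 57.7% | 19.2% |
| AR(1) 0.5 | 47.8% | 60.5% | 18.1% |
| AR(1) 0.7 | 53.9% | 65.2% | 16.0% |
| Exchangeable 0.3 | 54.2% | 65.4% | 16.7% |
| Exchangeable 0.7 | 66.4% | 75.5% | 11.3% |

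Any-window error at 45/90 is nearly the same (11.3–20.3%).

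**Pilot reductions (Table 2, 10 BESB vs 20 ERAS).**
- Mean OME: 48 h, 1 − 0.854/1.134 = 24.7%; 96 h, 1 − 1.346/1.557 = 13.6%.
- Square root: 48 h, 1 − 0.890/1.050 = 15.2%; 96 h, 1 − 1.120/1.231 = 9.0%.
- At the pilot 96 h difference, 1.231 − 1.120 = 0.111 with SD 0.32, power is 41% at 38/76 and 47% at 45/90.

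**Scale of the 15%.** A 15% fall in the square root is 1 − 0.85² = 27.8% in OME. Conversely, 15% of OME is 1 − √0.85 = 7.8% on the square-root scale:
- 96 h: 1.231 × 0.078 = 0.096, SD 0.32; power 32% at 38/76 and 37% at 45/90.
- 48 h: 1.050 × 0.078 = 0.082, SD 0.26; power 35% and 40%.

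**The case against.** The best defence is that Section L does give one explicit efficacy criterion, at 96 hours, and that the 0–96 h total follows from windows already listed. Also, 48 h is both listed and powered. This narrows the point but does not remove it: a sample-size section does not replace the endpoint definition, and Sections A, B and E all give five windows.

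A reader might infer that any single significant window would count as success, with a false-positive risk of 11–20%. No section says so. Section A's wording is conjunctive and Section L names 96 hours. The reading is merely not excluded, so the central conflict is 96 h alone against all five.

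A reader might also take the low-correlation rows as the realistic ones, because Table 2's 96 h to 48 h variance ratio (0.540²/0.390² = 1.92 in ERAS; 0.724²/0.528² = 1.88 in BESB) is nearest to theirs. That match depends on equal block variances, which is doubtful: mean ERAS use from 48 to 96 h is 1.557 − 1.134 = 0.423, or 37% of the first 48 h. With smaller late variances, ratios of about 1.9 arise with any-window error from 11% to 18% and all-five power at 38/76 from 48% to 66%. Table 2 does not locate the truth within the ranges.

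It is likewise tempting to settle the measure as rescue opioid. Section B calls the primary rescue, and the pilot result "resulted in an approximate 25% reduction in rescue opioid requirements in the first 48 hours amongst the BESB group" agrees with Table 2's 24.7%. But Section A says consumed, Section E's primary is unqualified, and Section L mixes total with rescue.

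Finally, matching is blinded to outcomes, and Section N presents the study as possible groundwork for a randomised trial. That tempers the consequence; it does not supply a primary endpoint.

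**Conclusion.** The point stands and must be fixed. The plan does not determine which opioid result decides efficacy, and its 80% power is correct arithmetic for an outcome on neither endpoint list. If all five windows are required, joint power is about 42–66% at 38/76 and 55–76% at 45/90. These ranges rest on assumed block correlations of 0–0.7 and an equal standardised effect of 0.5625 in every window, and are illustrations. The pilot contrast between 48 h and 96 h shows that the choice can matter, but with 10 and 20 patients it is indicative only. The documents do not support saying that one window suffices, or that the primary is definitely rescue or definitely total opioid.

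**What to change.** Name one primary endpoint, worded identically in Sections A, B, E, K and L. Make the other windows secondary, in a fixed testing order or as estimates with 95% confidence intervals. Either option is workable:

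- **Cumulative 0–48 h OME.** Already listed; 87% power at 38/76 and 92% at 45/90 for a 0.16 difference. Section L's efficacy definition and sample-size basis must be restated.
- **Cumulative 0–96 h OME, added to Section E.** Matches Section L; 80% at 38/76 and 86% at 45/90 for a 0.18 difference, but only 41% and 47% at the pilot difference. It needs an analysis rule for patients discharged before 96 hours. Section D(3) has the watch worn "until discharge from the hospital (which on average is about 5 days post-op", and the share leaving earlier is not given.

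If all five stay primary, state the any/all rule and the alpha for each, and restate the power. For example, 0.01 per window leaves 58% power per window at 38/76 and 68% at 45/90 for the planned standardised effect.

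In the same edit, state whether the primary is rescue or total OME, the analysis scale, and the scale on which the 15% applies.

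Cost: the remaining windows lose primary status. No extra patients or data are needed if the 15% stays on the square-root scale. If 15% of OME itself is meant, the power must be restated.

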### **Secondary:**

- Analgesic requirements, rendered as total opiate equivalents, at 12, 24 and 48 hours, and the 24-hour period preceding both 72 and 96 hours postoperatively.
- Duration of intubation following OR exit.
- Duration of ICU stay following OR exit.
- Duration of inpatient admission.
- Median pain scores collected per standard of care (VAS, NRS, INRS, or FLACC) at 0-3h, 3-6h, 6-12h, 12-24h, 24-36h and 36-48h.
- Incidence of postoperative nausea and vomiting during the following time ranges: 0-6h, 6-12h, 12-24h, and overall
- Time to mobilization (e.g. up to chair, ambulation).
- Quality/Quantity of mobilization and sleep via postoperative actigraphy.
- Outcome and satisfaction measures associated with routine perioperative questionnaire responses.
- Adverse events. – catheter, hemodynamic instability during placement (new inotrope or vasopressor – including Ca, volume > 5ml/Kg, variation 10% baseline SBP and MAP)
- All major Society of Thoracic Surgeons (STS) standard indices of morbidity and mortality

\*Of note, all of the above data points are collected automatically (via the electronic medical record) for all patients, as a part of their routine clinical care, regardless of whether or not they participate in the study.

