## **D. Design and Methods**

### **(1) Study Design**

We propose a single arm, open label, interventional study to compare the opiate requirements of 45 patients who consent to receive BESB catheters following cardiac surgery via sternotomy versus 90 matched historical controls who had similar surgical procedures but without BESBs.

Patients meeting eligibility criteria will be recruited and enrolled to have BESBs placed for postoperative pain control as a part of their perioperative anesthetic

plan. These patients will subsequently have a variety of preoperative demographic and functional data collected as well as data related to their surgeries and postoperative course all collected for later analysis. This enrolled group of patients will subsequently be compared regarding these outcome measures with a 1:2 matched, retrospective analysis of patients in the cardiac surgical ERAS program who did not receive regional blocks as a component of their anesthetic care. (The ERAS Cardiac program is a heart center perioperative evidence-based quality initiative. Retrospective data analysis of outcomes for patients in this program is performed for quality improvement purposes and outcomes research [IRB P00029161 – PI: [name] MD, co-investigators: [name] MD, [name] MD]). Children aged 2 years through 17 years meeting entry criteria will be screened and recruited for participation from the Boston Children's Hospital cardiac surgical program.

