### **(3) Description of Study Treatments or Exposures/Predictors**

Participants will have their medical record reviewed following enrollment for demographic information including: gender, age, weight and height, procedure, surgeon, and current and historical medication use.

Any other routine standard-of-care data will be collected preoperatively as well in addition to research-specific data points.

All enrolled patients will have bilateral erector spinae blocks (with catheters for postoperative local anesthetic infusion) placed by the by a member of the BCH regional anesthesia team (under the supervision of a member of the research team) in a sterile fashion after the cardiac surgical procedure is completed. The placement is as follows:

- The patient is placed in a lateral decubitus position (left or right), with all pressure points padded in routine fashion.
- The area for intervention is prepped with a chlorhexidine solution, and sterile drapes are applied to demarcate the block placement area.
- The T4/5 transverse process on one side is identified with the ultrasound transducer in a parasagittal orientation.
- An 18g Tuohy needle is advanced to the target area under direct ultrasound visualization. The needle tip is advanced until it contacts the transverse process, just below the erector spinae muscle complex.
- Normal saline is injected to confirm appropriate needle tip position. The erector spinae muscle is visualized to be elevated up off of the transverse process with normal saline injection
- With confirmation of appropriate needle tip position, the initial local anesthetic bolus is injected using a standard, weight-based dosing protocol.

- Following the bolus injection, a catheter is threaded into the space occupied by the local anesthetic bolus.
- Catheter tip position is verified by one or more of the following: ultrasound visualization of the catheter tip, ultrasound visualization of instilled normal saline and/or ultrasound visualization of a small hyperechoic (i.e. bright on ultrasound) injection of air.
- With the catheter tip position identified, the catheter is tunneled to a cutaneous exit point approximately 2-3cm from the incision using a Crawford needle.
- The catheter is dressed in standard fashion with an adhesive catheter anchor, Dermabond, Mastisol, Tegaderm and tape.
- This is repeated for the contralateral side. To the extent possible, this will be done without repositioning in a contralateral decubitus position.

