Ropivacaine use constitutes the standard of care at BCH for all nerve blocks and regional anesthetics, including cardiac surgical ERAS patients. Known potential adverse consequences of this mode of delivery of this medication include hypersensitivity, allergic reaction, hypotension and cardiac arrhythmias if injected intravascularly. The presence of any of these will be assessed by the primary anesthesiologist intraoperatively and treated appropriately at the time of block placement and initial bolus and further assessed for such daily by members of the research team and Acute Pain Service. Any occurrence of a possible adverse event or events will be documented and reported to the DSMB, the IRB and the Department of Anesthesia Quality Assurance Physician as appropriate. In the event

of a serious adverse event, it will be reported to the DSMB and IRB immediately and the study halted until a thorough investigation into the cause can be made.

The relative safety of ropivacaine for use in regional anesthesia is supported by the information contained the Pediatric Regional Anesthesia Network (PRAN) database. The PRAN is a consortium of major pediatric centers in North America that manages a prospective data registry on pediatric regional anesthesia. From their database, which at this time comprises more than 130,000 pediatric regional anesthetics from numerous major centers in the US and Canada, ropivacaine is documented to be used in greater than 85% of pediatric regional with a safety profile at least equivalent to, if not better than, bupivacaine.

Further, ropivacaine is very well studied in pediatrics. There is an extensive body of prospective clinical trials and clinical outcomes studies on ropivacaine pharmacokinetics, safety and clinical outcomes from infancy through adolescence. Our prescribing practices at BCH in the Regional Anesthesia and Acute Pain Services are derived from that body of PK information and consensus recommendations.

We therefore regard ropivacaine as the established standard of care for pediatric regional anesthesia and have selected it for use in this study.

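### Intubation time is counted from OR exit, so the time spent placing the block, which only BESB patients have, falls outside the endpoint and the comparison leans towards BESB

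*Combined protocol and SAP*

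**What the plan says.** - **Endpoint.** Section E, Secondary, lists "Duration of intubation following OR exit". This is the only place where a starting point for intubation time is given.
- **When the block is placed.** Section D(3) has every enrolled patient receive bilateral catheters "in a sterile fashion after the cardiac surgical procedure is completed", lying in lateral decubitus.
- **Where, and for how long.** Section B reports that the 10-patient pilot found the blocks "technically feasible, requiring 30 minutes or less of OR time, resulting in no known complications"; Section C repeats the time. The ropivacaine note in Section I treats placement as part of the intraoperative period: reactions "will be assessed by the primary anesthesiologist intraoperatively and treated appropriately at the time of block placement".
- **Controls.** Section D(1) draws them from ERAS patients "who did not receive regional blocks as a component of their anesthetic care".
- **Aim.** Aim 3 compares "duration of mechanical ventilation, time to mobilization" and other outcomes between the groups, with no time origin.
- **Analysis.** Section K lists time to extubation, again without an origin, and lists block placement time as a separate variable. Nothing adds the second to the first.

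**The concern.** A fair comparison of durations needs a starting point that treatment cannot move. Here it can. Placement happens between the end of surgery and OR exit, so BESB patients reach the start of the clock later, relative to the end of surgery, than they would have without the block. Controls have no such step.

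If the time from end of surgery to extubation were the same in both arms, the BESB arm would still show a shorter intubation time, by the length of the block procedure. The error runs one way, towards a benefit that Sections B and N put forward (earlier extubation). Matching on procedure, diagnosis, age and gender cannot remove it, nor can the planned check on bypass and clamp times, because the interval arises after surgery and comes from the intervention itself.

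**Working it through.** **The plan's own figures.** The plan gives no mean, SD, sample size or power for intubation time. Its only calculation is for opioid use (Section L), and it reproduces:
- 96 h: BESB n = 1.5 × (1.96 + 0.842)² × 0.32² / 0.18² ≈ 37.2, so 38 and 76, as stated.
- 48 h: SE = 0.26 × √(1/38 + 1/76) = 0.0517; power = Φ(0.16/0.0517 − 1.96) ≈ 87%, as stated.

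Neither figure bears on intubation time.

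**The offset.** Let T be the time from end of surgery to extubation, B the block time, and G any other OR time after surgery, taken as equal on average in the two arms (the documents give no OR times). The endpoint records T − G − B for BESB and T − G for controls. The measured difference in means is therefore the true difference in T minus the mean of B. On the pilot figure B lies between 0 and 0.5 h.

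- If T is the same in both arms, the endpoint shows a reduction equal to mean B that is not there when counted from end of surgery.
- If the course after OR exit is what stays the same (for example, weaning begins only on ICU arrival), the endpoint shows no difference. The spurious reduction is then zero, but the added intubated time in the BESB arm goes uncounted.

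**Conditional illustration.** Inputs: 45 vs 90 (planned enrolment, Section L); two-sided 5%; no true difference in T; shift d = 0.5 or 0.25 h in every BESB patient (assumed); SD of intubation time assumed.

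SE = SD × √(1/45 + 1/90) = 0.1826 × SD. Rejection favouring BESB = Φ(d/SE − 1.96). Two-sided rejection adds Φ(−d/SE − 1.96).

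Worked case, SD 1 h and d = 0.5 h: d/SE = 2.74, and Φ(2.74 − 1.96) = Φ(0.78) ≈ 78%.

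| Assumed SD (h) | d = 0.5 h: favouring BESB / two-sided | d = 0.25 h: favouring BESB / two-sided |
|---|---|---|
| 1 | 78.2% / 78.2% | 27.7% / 27.8% |
| 2 | 27.7% / 27.8% | 10.1% / 10.5% |
| 3 | 14.8% / 15.0% | 6.6% / 7.4% |
| 4 | 10.1% / 10.5% | 5.3% / 6.4% |
| 8 | 5.3% / 6.4% | 3.7% / 5.3% |
| 12 | 4.2% / 5.5% | 3.2% / 5.1% |

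Nominal values are 2.5% and 5%. At 38 vs 76 the two-sided figures for d = 0.5 h are slightly lower: 71.1%, 24.2%, 13.4% and 9.6% at SD 1, 2, 3 and 4 h.

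For scale, the difference detectable with 80% power at 45 vs 90 is 0.51 h at SD 1 h, 1.02 h at SD 2 h, 2.05 h at SD 4 h and 4.09 h at SD 8 h. The offset is about as large as a detectable effect when extubation times are tightly spread, and small beside it when they are not.

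**The case against.** The strongest reply is that this is a choice of estimand. The endpoint is openly labelled, uses the same event in both arms, and answers a legitimate question: how long patients stay ventilated after leaving the OR. Read that way, a shorter interval is not false. This stands as far as it goes. But Aim 3 promises a comparison of mechanical ventilation, and the OR-exit interval leaves out part of it in one arm.

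Block placement time is also already an analysed variable in Section K, so a careful reader of the results could add it back. That is true, but the plan does not do so.

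Several stronger readings are tempting and are not supported:
- *ICU stay is biased in the same way.* A reader might infer this because Section E also lists "Duration of ICU stay following OR exit". But ICU stay cannot begin before OR exit, so no ICU time is lost in either arm. Starting it at end of surgery would count OR time as ICU time, against BESB.
- *Every BESB patient loses 30 minutes.* The figure is an upper value seen in 10 pilot patients. It is neither a mean nor a limit set for this trial.
- *Controls leave the OR at once, and BESB patients are certainly intubated throughout placement.* Neither is stated. Lateral positioning, intraoperative anaesthesia care and the mention of extubation only later, on the day of surgery (Section D(3)), make the second likely. Control OR times are not given, so the net added OR time cannot be checked.
- *A false positive is likely.* The rejection rates rest on assumed SDs and a comparison of means. Section K switches to a rank test if the data are not normal, and then these rates would not apply as they stand.

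**Conclusion.** The concern holds for intubation time only. The intervention moves the starting point of the endpoint in one arm, always in the direction that favours BESB, and nothing in the matching or in Section K corrects it. The size is 0 to about 0.5 h in the mean. It rests on three assumptions: patients are intubated during placement, block times are like the pilot's, and other OR time after surgery is similar in the two arms.

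Whether that matters for inference depends on a spread that the documents do not give. It could be decisive at an SD near 1 h, is modest at 3 to 4 h, and is negligible at 8 h or more. This is a secondary endpoint with no power calculation of its own; the opioid outcome and the 38/76 calculation are untouched. The change is worth making because it is cheap and removes a bias of known direction.

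**What to change.** - In Section E, define duration of intubation in both arms as the time from the recorded end of surgery (for example, skin closure) to extubation.
- Use the same origin in Aim 3 and Section K, so that mechanical ventilation, intubation and time to extubation mean one thing.
- Keep OR exit to extubation as a supplementary figure, and report block placement time beside it.
- Leave ICU stay timed from OR exit.

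The cost is a wording change and one extra EMR timestamp per patient, for up to 45 + 90 = 135 patients. Section D(3) already plans to take intraoperative data from the EMR. Patient care and sample size do not change. The BESB result may look slightly less favourable.
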